10.2 Investigational device application methods

[Investigational devices]

Medifoam[®] (Mundipharma)

Betafoam[®] (Mundipharma)

[General investigational device application method]

An appropriate type of the investigational device should be selected for the study ulcer size and it should be able to completely cover the target pressure ulcer. At every dressing change, record the selected investigational device size in the source document.

[Investigational device application sequence]

- ① Carefully wash the target pressure ulcer with normal saline.
- ② After washing, wipe the study ulcer for drying with sterilized gauze, if necessary. At this time, pay attention not to irritate the study ulcer.
- ③ Select a study device that is larger than the pressure ulcer, open the product packaging, take out the device using tweezers, and remove the release film. Directly cover the wound with the foam side without the release film, paying attention to completely cover the wound.
- ④ If necessary, fix around the edge of this product with surgical tape or Band-Aid while paying attention not to attach too tight to avoid skin irritation.
- ⑤ If there is a lot of exudate and a leak is likely to occur at the study ulcer, exchange the dressing more frequently than planned (twice weekly).

[Application frequency]

- Twice weekly

During the 12-week treatment period, dressing is performed twice weekly, but additional dressing changes are allowed, depending on the condition of the pressure ulcer, such as excessive exudates at the lesion. Nevertheless, the frequency of additional dressing is limited to twice per day. In case of additional dressing changes beyond twice weekly changes, the change frequency should be recorded in the Case Report Form.

On the weekly site visit days, the investigator (or clinical research coordinator) will change the dressing; on other occasions, the subject or guardian will perform self-dressing. The investigator (or clinical research coordinator) will train the subject or guardian on the dressing method at every visit.

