12.1.2 Visit 2 (enrollment, 1d)

Subject enrollment will take place at the second visit, and the following assessment will be conducted.

- ① Conduct the physical examination.
- ② Review the inclusion/exclusion criteria, and subjects who are finally determined eligible will go through the process of randomization.

- ③ Before applying the investigational device, check the infection signs using the CSSC(Clinical Signs and Symptoms Checklist).
- ④ Before applying the investigational device, take a photograph of the study ulcer, investigator will conduct a photo evaluation, and record the pressure ulcer size by a Scale.
- ⑤ After conducting standard dressing, apply the investigational device.
- ⑥ Record the baseline PUSH score.
- ⑦ Review concomitant medication and treatment-emergent adverse events.
- ⑧ Prescribe the investigational devices and train the subject or guardian on the self-dressing method.
- ⑨ Dispense the subject diary to record the frequency of position changes per day (if applicable) and the frequency of additional self-dressing.

12.1.3 Visit 3, 4, 5, 6, 7, 8, 9, 10, 11, 12, 13 (interim visit, 8d, 15d, 22d, 29d, 36d, 43d, 50d, 57d, 64d, 71d, 78d)

The following tests will be conducted at the interim visit. It can be replaced by home health care through coordinator's visit if the subject is not able to visit the institution.

- ① Conduct the physical examination.
- ② As vital signs, measure blood pressure, pulse, and body temperature.
- ③ Measure body weight (only 29d).
- ④ After removing the investigational device, take a photograph of the study ulcer, conduct the investigator's photo evaluation, and record the pressure ulcer size by a Scale and complete healing status.
- ⑤ Check the infection signs using the CSSC (Clinical Signs and Symptoms Checklist).
- ⑥ After conducting standard dressing, apply the investigational device.
- ⑦ After conducting the pressure ulcer assessment, record the PUSH score (15d, 29d, 43d, 57d, 71d).
- ⑧ Review concomitant medication and adverse events (all adverse events, local adverse events at the study ulcer).
- ⑨ Prescribe the investigational devices and train the subject or guardian on the self-dressing method.
- ⑩ At the last visit, investigational devices that have been prescribed but not used are to be returned.
- ⑪ Based on the subject diary, record the frequency of self-dressing beyond once-weekly in the Case Report Form.

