12.2.9 Self-dressing training and frequency review

As a subject is to perform dressing twice weekly by himself/herself or a guardian, the investigator (or clinical research coordinator) will train the subject or guardian on standard dressing for self-dressing at every visit. Depending on the condition of the pressure ulcer such as excessive exudates, a subject may conduct self-dressing more frequently than twice weekly. In case of conducting self-dressing beyond twice weekly, the subject should inform the investigator of the additional dressing frequency during the site visit, and the investigator will record the frequency of self-dressing beyond twice weekly in the Case Report Form.

Standard dressing method will be trained as follows.

- ① Carefully wash the target pressure ulcer with normal saline.
- ② After washing, wipe the study ulcer for drying with sterilized gauze, if necessary. In this process, pay attention not to irritate the study ulcer with the gauze.
- ③ Open packaging of the study device, take out the device using tweezers, and remove the release film. Directly cover the wound with the foam side without the release film, paying attention to completely cover the wound.
- ④ If necessary, fix around the edge of this product with surgical tape or Band-Aid while paying attention not to attach too tight to avoid skin irritation.
- ⑤ If there is a lot of exudate and a leak is likely to occur at the study ulcer, exchange the dressing more frequently than planned for self-dressing (once weekly).

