15.3 Analysis of efficacy endpoints

(1) Analysis of endpoints of main interest

- ① Number of patients with complete healing# of ulcer within 12 weeks
: Subjects who achieved complete healing and had early completion will be included.
- ② Time to complete healing# of ulcer within 12 weeks
: Time to complete healing is calculated as the number of days from baseline (1d).
(# The definition of complete healing: Epithelial tissue covering 100% of the study ulcer, no abrasion or ulceration, intact dermis and epidermis)
- ③ Pressure ulcer size reduction rate based on a scale at each time point

$$\text{Reduction rate} = \frac{\text{Pressure ulcer size on 1d}^* - \text{Pressure ulcer size at each time point from 8d to End-of-Study}^{**}}{\text{Pressure ulcer size on 1d}} \times 100\%$$

* Using a scale-based pressure ulcer area (cm²) measured prior to the study device application

** Using a scale-based pressure ulcer area (cm²) without re-epithelization*** measured at each time point after the study device application

(**Re-epithelization: New epithelial tissue covering the pressure ulcer, with no exudate, transudate, or avascular tissue)

- ① For subjects achieving complete healing within 12 weeks, present frequency and percentage.
 - ② For the time to 100% complete healing, analyze using the Kaplan-Meier method. Subjects not achieving 100% complete healing within 12 weeks will not be considered for evaluation for end point of main interest.
 - ③ For the pressure ulcer size reduction rate, present the mean and standard deviation.
- For the analysis for efficacy, conduct sub-analyses by use of local antibiotics and glucocorticoids for the pressure ulcer during the study.

(2) Analysis of other endpoints

- ① PUSH reduction rate at each time point

$$\text{Reduction rate} = \frac{\text{PUSH score on 1d} - \text{PUSH score at each time point}}{\text{PUSH score on 1d}} \times 100\%$$

- ② Dressing change frequency during the entire study period
: Calculated as the additional dressing frequency beyond twice weekly
- ③ Number of subjects with early completion due to complete healing during the study
- ④ Incidence of new infections at the pressure ulcer until Week 12 based on the CSSC

$$\text{Infection incidence} = \frac{\text{Number of subjects with at least 1 new infection** until Week 12, after the study device application}}{\text{Total number of subjects}} \times 100\%$$

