## 3. Study Design

---

[figure not shown]
This is a single-center, randomized, 2-arms, open-label pilot study.

Subjects who consent to the study will be assessed for eligibility with screening tests. Subjects can have a 2-week screening period.

After screening, subjects who meet the inclusion/exclusion criteria will apply Medifoam® or Betafoam® for 12 weeks, after randomization. Targeted subjects are outpatient clinic or hospitalized patients. Subjects will make once weekly site visits.

During the treatment period, dressing is performed twice weekly, but additional dressing changes are allowed, depending on the condition of the pressure ulcer, such as excessive exudates at the study ulcer. Nevertheless, the frequency of additional dressing is limited to twice daily. On the weekly site visit days, the investigator(or clinical research coordinator) will change the dressing; on other occasions, the subject or guardian will perform self-dressing. Subjects who achieve complete healing of the target pressure ulcer within 12 weeks will have early completion.

Efficacy assessment is conducted for a total of 12 times at a 1-week interval, after the investigational device application (8d, 15d, 22d, 29d, 36d, 43d, 50d, 57d, 64d, 71d, 78d, 85d). At each efficacy assessment, the investigator (or clinical research coordinator) should take a digital photograph of the target pressure ulcer and retain it as a source document.

---

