## (2) Other endpoints

- ① PUSH reduction rate at each time point

$$\text{Reduction rate} = \frac{\text{PUSH score on 1d} - \text{PUSH score at each time point}}{\text{PUSH score on 1d}} \times 100\%$$

- ② Dressing change frequency during the entire study period

: Calculated as the additional dressing frequency beyond twice daily

- ③ Number of subjects with early completion due to complete healing during the study
- ④ Incidence of new infections at the pressure ulcer until Week 12 based on the CSSC

$$\text{Infection incidence} = \frac{\text{Number of subjects with at least 1 new infection}^{**} \text{ until Week 12, after the study device application}}{\text{Total number of subjects}} \times 100\%$$

(\*\* Infection: Presence of 'Purulent exudates' or 2 or more symptoms of the CSSC. However, for subjects with an infection at baseline, it is defined as development of an additional symptom other than those confirmed at baseline or recurrence of baseline-identified symptoms after being completely healed.)

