## **(2) Analysis of other endpoints**

For other endpoints, present the mean, median, min, max and standard deviation for the continuous variable PUSH reduction rate at each time point, and frequency and percentage for categorical variables of Dressing change frequency, Number of subjects with early completion due to complete healing, and Incidence of new infections at the pressure ulcer after investigational device application. t-test and paired t-test will be conducted for PUSH reduction rate while Fisher's exact test will be used to see the difference between Medifoam and Betafoam for Dressing change frequency, Number of subjects with early completion, and Incidence of new infections.

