		Mean±Std	xx.xx±x.xx	xx.xx±x.xx	xx.xx±x.xx	
		Median	xx.xx	xx.xx	xx.xx	
		Min~Max	xx.xx~xx.xx	xx.xx~xx.xx	xx.xx~xx.xx	
	Visit4~Visit13	..(Middle Part Omitted)..				
	Visit14(85d±2d)	N	xx	xx	xx	0.xxxx*
		Mean±Std	xx.xx±x.xx	xx.xx±x.xx	xx.xx±x.xx	
		Median	xx.xx	xx.xx	xx.xx	
Min~Max		xx.xx~xx.xx	xx.xx~xx.xx	xx.xx~xx.xx		
Glucocorticoids Not used	Visit3(8d±1d)	N	xx	xx	xx	0.xxxx*
		Mean±Std	xx.xx±x.xx	xx.xx±x.xx	xx.xx±x.xx	
		Median	xx.xx	xx.xx	xx.xx	
		Min~Max	xx.xx~xx.xx	xx.xx~xx.xx	xx.xx~xx.xx	
	Visit4~Visit13	..(Middle Part Omitted)..				
	Visit14(85d±2d)	N	xx	xx	xx	0.xxxx*
		Mean±Std	xx.xx±x.xx	xx.xx±x.xx	xx.xx±x.xx	
		Median	xx.xx	xx.xx	xx.xx	
Min~Max		xx.xx~xx.xx	xx.xx~xx.xx	xx.xx~xx.xx		

Note) \*: t-test, ¥ : Wilcoxon rank sum test

7) Analysis of Other endpoints

Analysis Set: FAS

Table 0701 PUSH reduction rate at each time point compared to baseline

Time points		Medifoam	Betafoam	Total	P-value
Visit3(8d±1d)	N	xx	xx	xx	0.xxxx*
	Mean±Std	xx.xx±x.xx	xx.xx±x.xx	xx.xx±x.xx	
	Median	xx.xx	xx.xx	xx.xx	
	Min~Max	xx.xx~xx.xx	xx.xx~xx.xx	xx.xx~xx.xx	
	P-value(within)	0.xxxx			
Visit4~Visit13		..(Middle Part Omitted)..			
Visit14(85d±2d)	N	xx	xx	xx	0.xxxx*
	Mean±Std	xx.xx±x.xx	xx.xx±x.xx	xx.xx±x.xx	
	Median	xx.xx	xx.xx	xx.xx	
	Min~Max	xx.xx~xx.xx	xx.xx~xx.xx	xx.xx~xx.xx	
	P-value(within)	0.xxxx			

Note) \*: t-test, ¥: Wilcoxon rank sum test

Table 0702 Dressing change frequency per week during the entire study period for subjects on Medifoam

	Medifoam			
	Visits			
Number of Dressing Change per week	Visit3	Visit4	....	Visit14
None	N	N	N	N
One time	N	N	N	N
Two times	N	N	N	N
Three times	N	N	N	N
Four or more times	N	N	N	N
Total	N	N	N	N

Table 0703 Dressing change frequency per week during the entire study period for subjects on Betafoam

\*Same as 0702

Table 0704 Number of subjects with early completion due to complete healing during the study

		Medifoam	Betafoam	Total	P-value
		n(%)	n(%)	n(%)	
Early completion due to complete healing	Yes	xx(xx.xx%)	xx(xx.xx%)	xx(xx.xx%)	0.xxxx‡
	No	xx(xx.xx%)	xx(xx.xx%)	xx(xx.xx%)	
	Total	xx(xx.xx%)	xx(xx.xx%)	xx(xx.xx%)	

Note) ‡: Fisher's exact test

Table 0705 Number of subjects with CSSC signs and symptoms at each visit for subjects on Medifoam

CSSC signs and symptoms	Medifoam			
	Visit2	Visit3	....	Visit14
Increasing pain in the ulcer area	N	N	N	N
• Can't detect pain in ulcer area	N	N	N	N
• Have less pain now than in the past	N	N	N	N
• Intensity of pain remained the same	N	N	N	N

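### SAP 7.1 counts dressing changes beyond twice daily, but protocol 15.3 counts them beyond twice weekly, so coded as written the endpoint could be zero for nearly everyone

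*SAP*

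**What the plan says.** Protocol 10.1 and 10.2 plan two dressing changes a week for 12 weeks. One is made at the weekly visit and the other by the subject or guardian. Extra changes are allowed when the ulcer needs them, for example for heavy exudate.

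- **Endpoint, protocol 15.3 (2) item 2:** "Calculated as the additional dressing frequency beyond twice weekly".
- **Endpoint, SAP 7.1 (2) item 2:** "Calculated as the additional dressing frequency beyond twice daily".
- **Limit on extra changes, SAP Section 3:** "Nevertheless, the frequency of additional dressing is limited to twice daily". Protocol 10.1 and 10.2 set the same limit.
- **Analysis, SAP Section 8 (2):** the variable is treated as categorical, and Fisher's "exact test will be used to see the difference between Medifoam and Betafoam for Dressing change frequency".
- **Output, SAP Section 13, Table 0702:** "Dressing change frequency per week during the entire study period for subjects on Medifoam", by visit, with rows *None*, *One time*, *Two times*, *Three times* and *Four or more times*. Table 0703 repeats this for Betafoam.

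The protocol states the recording rule for the case report form (CRF) in several places:

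- **10.2:** "In case of additional dressing changes beyond twice weekly changes, the change frequency should be recorded in the Case Report Form".
- **12.1.3 item 11, repeated in 12.1.4:** "Based on the subject diary, record the frequency of self-dressing beyond once-weekly in the Case Report Form".
- **12.2.9:** "the investigator will record the frequency of self-dressing beyond twice weekly in the Case Report Form".
- **Synopsis (Dressing):** asks for the frequency to be recorded when the twice-per-day limit is exceeded.

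**The concern.** The two endpoint definitions match except for the threshold: two a week in the protocol, two a day (14 a week) in the SAP. The SAP appears to have taken the limit on extra changes as the point from which to start counting. Extra changes driven by exudate would normally fall between those two thresholds, and that is the range the SAP rule sets to zero. What remains would be mainly excess over the permitted limit, which describes compliance more than dressing need. If most or all subjects in both arms score zero, the planned comparison of the foams on this endpoint carries no information.

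**Working it through.** The plan states no figure for this endpoint, so there is none to reproduce. The check applies each definition to the same subject.

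**Inputs.** Planned changes: 2 a week (protocol 10.2). Protocol threshold: 2 a week (15.3). SAP threshold: 2 a day (SAP 7.1). T is the total number of changes in a week, one at the visit and T − 1 by self-dressing. T is an illustrative assumption, with changes spread evenly over the days.

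**Endpoint, additional changes per week.**

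- Protocol 15.3: max(0, T − 2)
- SAP 7.1: 7 × max(0, T/7 − 2)

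| T per week | Protocol | Row if excess is tabulated | SAP | Row if excess is tabulated |
|---|---|---|---|---|
| 2 | 0 | None | 0 | None |
| 3 | 1 | One time | 0 | None |
| 4 | 2 | Two times | 0 | None |
| 7 (daily) | 5 | Four or more times | 0 | None |
| 14 (twice daily) | 12 | Four or more times | 0 | None |
| 21 (three a day) | 19 | Four or more times | 7 | Four or more times |

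The definitions give different rows for the tabulated weeks from 3 to 14 changes. If the SAP threshold is applied only to changes already additional to the schedule, it is harder still to reach, and the zeros remain.

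**If the rows are raw weekly counts**, a daily changer (7 a week) appears under *Four or more times* whatever the definition. The table then keeps the information, but it no longer shows the endpoint that SAP 7.1 defines. The shells do not say which count is meant.

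**CRF recording rules, for T = 7 and T = 3.**

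- 10.2, total beyond two: 7 − 2 = 5; 3 − 2 = 1.
- 12.1.3 and 12.1.4, self-dressing beyond one: (7 − 1) − 1 = 5; (3 − 1) − 1 = 1. This is the same count as 10.2.
- 12.2.9, read literally as self-dressing beyond two: (7 − 1) − 2 = 4; (3 − 1) − 2 = 0. This is one short of 10.2 in any week with three or more changes. At T = 3 the row moves from *One time* to *None*.
- 12.2.9, read as total changes beyond two: 5 and 1, in agreement with 10.2.

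**The case against.** The best reply is that the intent is clear from the rest of the SAP. Section 11 says the analysis follows the protocol in principle. The table shells run per week, which suits a weekly threshold and not one of 14 changes a week. A careful programmer might therefore apply the protocol rule. This stands as evidence that the SAP wording is a slip, and it makes the all-zero endpoint a risk and not a certainty. It does not correct an explicit definition in the section that defines the endpoints.

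The scale is also modest. Protocol 16.2 foresees no formal test, and this is not an endpoint of main interest.

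Four stronger readings are tempting, and the documents do not support them:

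- **A daily changer would be reported as 0 instead of 60 over 12 weeks.** The arithmetic is right (12 × 5 = 60), but no planned table gives a 12-week total. The output is a weekly category.
- **Under the synopsis, changes at or below twice a day go unrecorded.** The synopsis requires recording above the limit. It does not say that smaller excesses are left out, and 10.2 requires them. It does mean that twice per day serves there as a recording trigger as well as a limit.
- **The rule in 12.1.3 and 12.1.4 conflicts with 10.2.** It gives the same count, because one planned change a week takes place at the visit.
- **Any gap can be recovered from the diaries.** Protocol 12.2.12 has the diary record self-dressing frequency, but schedule footnote 9 and the visit instructions in 12.1.2 and 12.1.3 refer to additional changes. The diary may carry the same ambiguity, and its form is not shown.

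**Conclusion.** The contradiction between SAP 7.1 and protocol 15.3 is real, and the SAP definition is wrong as written. Followed literally, it gives zero additional changes to every subject with no more than two changes on any day. If the table rows are excess counts, a daily changer moves from *Four or more times* to *None*, and the Fisher comparison could be empty. That outcome depends on the rule being coded as written and on few subjects exceeding two changes in a day; the documents give no expected frequency. The protocol's recording rules need a smaller clarification, in 12.2.9 and the synopsis.

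The point affects one endpoint in the *other* tier of a 20-subject exploratory pilot. The healing, ulcer-size and safety analyses are untouched. It should be corrected, but it does not threaten the study's main results.

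**What to change.** **SAP.** In 7.1 (2) item 2, replace twice daily with twice weekly. In Tables 0702 and 0703, label the rows as changes per week beyond the planned two, counting visit and self-dressing changes together.

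**Protocol.** In 12.2.9, state that the count is total changes beyond twice weekly or, equivalently, self-dressing beyond once weekly; step 5 of that section already gives planned self-dressing as once weekly. Bring the synopsis recording rule into line with 10.2. Sections 12.1.3 and 12.1.4 can stay as they are.

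**Cost.** One word and one row label (used in two shells) in the SAP, and two wording clarifications in the protocol. No new assessment is needed. If CRFs have already been completed, check which rule the site applied before relying on the counts, and do not assume that the diaries allow a recount.

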## 7.2 Safety Endpoints

The followings will be evaluated for safety assessment.

### 1) Adverse event

At every visit, review both local adverse events at the target pressure ulcer and other adverse events.

(Local adverse events at the target pressure ulcer: Erythema, edema, itching, flare, rash, others)

### 2) Vital signs

Vital signs are analyzed by measuring at every visit until study completion. Measured vital signs are blood pressure(), pulse, and body temperature. In addition, body weight is measured at screening, Week 4 and at the End-of-Study visit. Visits conducted outside of the site will not include body weight measurement.

### 3) Laboratory tests and physical examination

Laboratory tests are conducted at screening and study completion. For physical examination, normal/abnormal status of findings at screening is confirmed, and it is assessed whether the subject is eligible for study participation. Physical examination is also performed at every subsequent visit. Visits conducted outside of the site will not include physical examination.

---

## 8. Statistical Methodology by Endpoints

---

### Analysis of Efficacy Endpoints

#### (1) Analysis of endpoints of main interest

- ① For subjects achieving complete healing within 12 weeks, present frequency and percentage. Fisher's exact test will be performed to compare Medifoam and Betafoam treatment groups.
- ② For the time to 100% complete healing, analyze using the Kaplan-Meier method. Time table for subjects to 100% complete healing will be presented and the survival Plot will be shown as a figure. Subjects not achieving 100% complete healing within 12 weeks will not be considered for evaluation for end point of main interest though ulcer size reduction will be evaluated for those subjects.

- ③ For the pressure ulcer size by each time point, present the mean, median, min, max and standard deviation. t-test will be conducted to compare Medifoam and Betafoam, and paired t-test will be used to see the difference between each post visit and baseline(1d).
- ④ For the pressure ulcer size reduction rate, present the mean, median, min, max and standard deviation. t-test will be conducted to compare Medifoam and Betafoam.
- ⑤ For the analysis for efficacy, conduct sub-analyses by use of topical antibiotics and glucocorticoids for the pressure ulcer during the study. t-test will be performed to compare Medifoam and Betafoam, and paired t-test will be used to see the difference between post visits and baseline(1d).

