8.2 Exclusion criteria

- 1) Any study ulcer of the NPUAP Stage I, II or IV
- 2) Diabetic ulcer or Venous ulcer (or stasis ulcer)
- 3) Past history of surgical treatment within 1 year or irradiation at the target pressure ulcer within 1 year
- 4) Hypersensitivity reaction to this product or povidone-iodine
- 5) Hyperthyroidism or thyroid disorder requiring drug treatment
- 6) Signs of a current underlying systemic infection (sepsis/bacterial infection/tuberculosis) or cellulitis or osteomyelitis
- 7) Type 1 diabetes
- 8) Current malnutrition
- 9) Heavy smoker: Current smoking level of ≥ 1 pack (20 cigarettes)/day of tobacco
- 10) Drug or alcohol addiction
- 11) Requirement of immunosuppressants during the study or current chemotherapy or radiotherapy
- 12) Application of other investigational product/medical device within 1 month prior to the

investigational device application (1d)

13) Pregnant or breastfeeding women

14) Other renal, hepatic, neurological, immunological disorder that may interfere with the wound healing process, at the discretion of the investigator

9. Target number of subjects and the rationale

The target number of subject enrollment is 20 subjects, with 10 subjects per group.

This study has a purely explorative goal so that no formal sample size calculation will be conducted but it was planned to enroll 10 subjects per group as the minimum sample size to achieve study objectives from a scientific perspective.

- ✓ Medifoam group: 10 subjects
- ✓ Betafoam group: 10 subjects

Even if a subject is withdrawn from the study, the subject will not be replaced.

10. Study method

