15.2 Baseline demographics

For each study group and the entire group, the mean, standard deviation, minimum & maximum will be presented for continuous data, and absolute and relative frequency will be provided for categorical data. For baseline demographics, only descriptive statistics will be presented.

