16.2 Assessment criteria and methods

This study is a pilot study with no comparator, so that no formal statistical test will be conducted.

17. Safety assessment methods and criteria, and interpretation methods, including adverse events

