### Further Consideration

- In principle, the analysis shall follow the methods presented in Protocol No. BTF16-AP-401 and the general items regarding statistical analysis procedure shall be described.
- For continuous variables, Shapiro-Wilk test with p-value 0.05 will be used for normality test. t-distribution approximation method will be used for Wilcoxon rank sum test.
- Chi-square test will be used on half of Fisher's exact test in case when SAS 9.3 cannot handle the amount of test calculation.

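### SAP section 8 and its shells plan some 80 to 90 Medifoam vs Betafoam efficacy tests, plus baseline p-values, that the protocol does not provide for, and no between-arm difference with a confidence interval

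*SAP*

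**What the plan says.** Protocol 16.2: "This study is a pilot study with no comparator, so that no formal statistical test will be conducted". Protocol 15.2: "For baseline demographics, only descriptive statistics will be presented". Protocol 15.3 plans frequency and percentage for healing and Kaplan-Meier for time to healing, and for size: "For the pressure ulcer size reduction rate, present the mean and standard deviation". No test appears there. Protocol section 9 adds: "This study has a purely explorative goal so that no formal sample size calculation will be conducted".

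SAP section 11 says: "In principle, the analysis shall follow the methods presented in Protocol No. BTF16-AP-401". SAP section 8 nevertheless plans:

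- **Healing:** "Fisher's exact test will be performed to compare Medifoam and Betafoam treatment groups".
- **Ulcer size and reduction rate at each visit:** "t-test will be conducted to compare Medifoam and Betafoam". Paired t-tests against 1d are added for size.
- **Sub-analyses by topical antibiotic and glucocorticoid use:** t-tests and paired t-tests.
- **Other endpoints:** t-tests and paired t-tests for PUSH. In addition, "Fisher's exact test will be used to see the difference between Medifoam and Betafoam for Dressing change frequency", and likewise for early completion and new infections.

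The shells go further. Table 0602 has a p-value for healing time that the section 8 text does not mention, and Table 0604 has a within-arm p-value. Table 0201 has 13 baseline p-values, and Tables 0301-0303, 0306, 0401 and 0502 have more. The only efficacy confidence interval is the per-arm infection rate in Table 0707.

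**The concern.** The two documents give different answers on whether the arms are tested against each other. An analyst cannot follow both as written, and the SAP neither explains the change nor says how its p-values are to be read. It sets no significance level for them (its only 0.05 belongs to the Shapiro-Wilk check) and does not mention multiplicity.

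Protocol 5.1 says a further trial will be built on this result. At 10 per arm, isolated p-values are a poor basis for that. A single healing test can easily miss a large difference, while a run of visit-wise tests can produce a chance one. The quantity a planner needs, an estimated difference with its uncertainty, is not pre-specified. It could be derived later from the arm-level summaries, but the choice of endpoint and visit would then be made with the data in view.

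**Working it through.** **1. What can be reproduced.** The 20 subjects (10 per arm) have no calculation behind them, so there is nothing to reproduce. The 12 efficacy visits do reproduce: 8 + 7k days for k = 0 to 11 ends at 85.

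**2. Count of post-baseline between-arm efficacy tests.**

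| Source | Tests |
|---|---|
| Healing (Table 0601) | 1 |
| Healing time (Table 0602, shell only) | 1 |
| Size (Table 0603) | 12 |
| Reduction rate (Table 0604) | 12 |
| Drug-use strata (Tables 0605-0606): 2 drugs x 2 strata x 12 visits | 48 |
| PUSH, six days in Protocol 12.2.11 | 6 |
| Dressing changes, early completion, infection | 3 |
| **Total** | **83** |

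Other counting rules:

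- Dropping dressing changes and infection, whose shells have no p-value column, gives 83 - 2 = 81.
- Also taking PUSH at all 12 visits that Table 0701 spans gives 81 + 6 = 87, or 88 with the 1d row of Table 0603.
- Taking 83 and adding PUSH at 12 visits (+6), dressing changes tested per visit (+11) and the 1d size row (+1) gives 101. This is not a proven ceiling, because the shells omit rows.

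Outside the strata there are 83 - 48 = 35 tests. Suppose a stratum test needs at least 2 subjects per arm. Then about 24, 26, 33 and 47 of the 48 can be computed at assumed drug use of 5, 10, 20 and 50%, giving totals of about 59, 61, 68 and 82.

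**3. Fisher's test at 10 vs 10** (exact enumeration, two-sided 0.05 assumed because the SAP states no level).

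- Size at a common healing rate of 20, 30 and 50%: 0.8, 1.2 and 1.3%.
- Power: 12% for 30% vs 60%, 25% for 20% vs 60%, 43% for 20% vs 70%, 64% for 20% vs 80%.
- The smallest significant split from zero is 0 vs 5 healed (p = 0.033); 0 vs 4 gives p = 0.087.

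**4. Twelve visit-wise t-tests of reduction rate, no true effect** (20,000 simulated trials, normal data, AR(1) correlation between visits). At least one p<0.05 occurs in about 30, 22, 17, 12 and 9% of trials at correlation 0.8, 0.9, 0.95, 0.98 and 0.99. Visit 14 alone gives about 5%.

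**5. What an interval would show.**

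- Illustrative 3/10 vs 6/10 healed: Fisher p = 0.37. Wilson limits are 0.108 to 0.603 and 0.313 to 0.832. Newcombe lower limit = 0.30 - sqrt((0.6 - 0.313)² + (0.603 - 0.3)²) = -0.12. Upper limit = 0.30 + sqrt((0.832 - 0.6)² + (0.3 - 0.108)²) = 0.60. Exact per-arm intervals are 7 to 65% and 26 to 88%.
- Mean difference in reduction rate: half-width = t(18) x SD x sqrt(2/10) = 2.101 x 0.447 x SD = 0.94 SD. That is 23.5 points at an assumed SD of 25 and 47 points at an SD of 50.

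**The case against.** Protocol 16.2 excludes a formal test, and its stated reason is the absence of a comparator. The SAP describes an exploratory aim and sets no efficacy alpha, power or decision rule, so a sponsor may say that its p-values are nominal. That is a fair reading. A reader might infer that 16.2 forbids every p-value, and the wording does not go that far. But the SAP never declares its tests informal, and Protocol 15.3 lists none. Protocol 15.2 leaves no such room for baseline demographics. The no-comparator reason also does not fit a randomised two-arm design, so the protocol sentence needs correcting too.

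A reader might also infer that 83 tests make a false positive almost certain: 1 - 0.95^83 = 98.6%. The documents do not support that figure. It assumes independence, whereas visits on the same subjects are correlated, Fisher's test is conservative, and many stratum tests may not be computable, since both drug classes are on the prohibited list with exceptions.

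The power and error figures rest on chosen inputs, because the documents give no healing rates, SDs or correlations. The simulation also leaves out the SAP's normality check and Wilcoxon alternative. Hence the ranges.

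The missing interval is not a breach of the protocol, which plans no between-arm contrast; adding one is a recommendation. Twelve unadjusted intervals would exclude zero as often as the twelve tests reach p<0.05.

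Finally, a reader might call the raw-size comparison invalid because it ignores 1d size. Randomisation keeps it valid, though less precise, and the reduction rate already scales to 1d size.

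**Conclusion.** The point holds. The baseline p-values contradict Protocol 15.2. This is plainest for Table 0201; the other baseline tables follow the same pattern. The efficacy tests do not match Protocol 15.3, and they conflict with 16.2 for as long as they are not declared informal.

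The size is about 80 to 90 planned between-arm tests (83 by direct count, 35 outside the drug-use strata), plus the within-arm paired tests, which were not counted. With 10 per arm and an assumed 0.05 level, the healing test has a size of about 1% and power of 12 to 25% for 30% vs 60% and 20% vs 60%, rising to 43 to 64% for 20% vs 70 to 80%. The visit-wise reduction-rate tests carry a 9 to 30% chance of at least one nominally significant result under no effect, across assumed correlations of 0.99 to 0.8.

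This does not invalidate the pilot. It is an inconsistency that should be settled before the report is written, because it decides what the report may claim.

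**What to change.** 1. Reconcile SAP section 8 and the shells with Protocol 15.2, 15.3 and 16.2.
   - Delete the baseline p-values (Tables 0201, 0301-0303, 0306, 0401 and 0502).
   - Either delete the between-arm and within-arm efficacy p-values, including those in Tables 0602 and 0604, or label them nominal and descriptive, with no significance claims.
   - Keep the arm-level summaries and the Kaplan-Meier display.
2. Correct the no-comparator wording in Protocol 16.2 so that it fits the randomised two-arm design.
3. As descriptive SAP additions, not to be read as tests:
   - in Table 0601, per-arm healing with an exact 95% CI and the risk difference with a 95% CI (Newcombe, for example);
   - in Table 0604, the mean difference in reduction rate with a 95% CI at Visit 14, which matches the 12-week objective in SAP section 2. State that intervals at any other visit are not adjusted for multiplicity.

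The cost is edits to the SAP, the shells and one protocol sentence, using data already planned for collection. The sponsor gives up any claim of statistical significance from this pilot.
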